8.1.2. Sensitivity Analyses of Primary Efficacy Endpoints

8.1.2.1. Last Observation Carried Forward

The primary efficacy analyses will also be performed using LOCF imputation as a sensitivity analysis. This analysis will use the ITT Set.

The change from baseline in MGYLS and OSDI total scores will be analyzed as described in [Section 8.1.1](#), based on observations using LOCF imputation as described in [Section 5.3.2](#).

8.1.2.2. Evaluation of Potentially Confounding Medications/Therapies at Month 3

The use of potentially confounding medications or therapies at Month 3 will be evaluated by tabulating the number of patients with medications that potentially affect Month 3 OSDI results, and, if a sufficient number of patients meet those criteria, repeating the OSDI analysis with a dichotomous variable indicating the presence/absence of such medications or therapies.

Potentially confounding medications or therapies will be identified as those having a Grade 4 protocol deviation with deviation class of concomitant medications/therapies. The duration of the deviation will include both the duration of medication/therapy usage and the subsequent washout period. Therefore, any such deviation whose start and stop dates overlap with the Month 3 visit date record on the Study Visits eCRF, will classify that patient as having a potentially confounding treatment for the Month 3 visit.

The number of patients with potentially confounding treatments at the Month 3 visit will be tabulated. Those patients will also be flagged in listings. If >10% of patients in the ITT Set have potentially confounding treatments at Month 3, an additional sensitivity analysis of the OSDI change from baseline will be performed. Specifically, the change from baseline in OSDI will be analyzed using an ANCOVA model similar to that described in [Section 8.1](#), with baseline MGYLS score as a covariate and treatment, duration of disease category, and baseline MGS score category as factors, with the presence of a potentially confounding treatment at Month 3 (i.e., yes or no) as an additional factor in the model. This analysis will be performed on the ITT Set, using multiple imputation.

The following pseudocode will be used:

```
PROC GENMOD data=xxx;  
  Where visit='Month 3';  
  CLASS treatment (ref = 'AZR-MD-001 PLACEBO') duration baseMGS;  
  MODEL chg =treatment base duration baseMGS confound;  
  LSMEANS treatment;  
run;
```

If this analysis is performed, the p-value associated with the presence of potentially confounding treatment will be presented in conjunction with the other OSDI results, and the least squares means and treatment differences from this model will be presented.

8.2. Secondary Efficacy Endpoints and Analyses

The following endpoints will be presented using the ITT Set. Multiple imputation will be applied, as described in [Section 5.3](#). These analyses will include all data collected through Month 3.

8.2.1. Key Secondary Efficacy Analyses

Proportion of MGYLS responders based on change from baseline ≥ 5 will be analyzed through Month 3 using a CMH test to compare the proportions between each AZR-MD-001 group and placebo, stratifying by disease duration category (i.e., <5 or ≥ 5 years) and baseline MGS score category (<6 or ≥ 6 and ≤ 12). If the CMH statistic is not estimable, the treatment difference will be evaluated using Pearson's chi-square test, or Fisher's exact test (if the expected cell count is <5 for at least 25% of the cells).

The following pseudocode will be used:

```
PROC FREQ data=xxx;  
  BY visit;  
  TABLE baseMGS * duration * treatment * response/CMH;  
  ODS OUTPUT CMH = outcmh (where=(STATISTIC=2));
```

```
Run;

PROC FREQ data=xxx;
  BY visit;
  TABLE treatment * response/EXACT;
  ODS OUTPUT CHISQ = outc (where=(STATISTIC='Chi-Square'))
             FISHERSEXACT=outf (where=(NAME1='XP2_FISH'));
Run;
```

Proportion of OSDI responders based on OSDI total score <13 will be analyzed through Month 3 as described for the proportion of MGYLS responders, using a CMH test (or chi-square/Fisher's Exact if CMH is not estimable) to evaluate the difference between treatments, controlling for duration of disease category and baseline MGS score category.

Change from baseline in SPEED score at Day 14, Month 1.5 and Month 3 will be analyzed as described for MGYLS in [Section 8.1.1](#).

Change from baseline in Eye Dryness VAS at Day 14, Month 1.5 and Month 3 will be analyzed as described for MGYLS in [Section 8.1.1](#).

8.2.2. Secondary Efficacy Analyses

Change from baseline in MGS will be analyzed through Month 3 using an ANCOVA model with (continuous) baseline MGS score as a covariate and treatment (AZR-MD-001 ointment/semi-solid drug or placebo) and duration of disease category (i.e., <5 or ≥5 years) as factors in the model. This ANCOVA model will be performed for each AZR-MD-001 ointment/semi-solid drug dosing level versus placebo. The least square means for the differences between treatments will be presented along with two-sided (95%) confidence intervals.

The following pseudocode will be used:

```
PROC GENMOD data=xxx;
  BY visit;
  CLASS treatment (ref = 'AZR-MD-001 PLACEBO') duration;
  MODEL chg =treatment base duration;
  LSMEANS treatment;
run;
```

Proportion of MGS responders based on MGS >12 will be analyzed at Day 14, Month 1.5, and Month 3 as described for the proportion of MGYLS responders, using a CMH test (or chi-square/Fisher's Exact if CMH is not estimable) to evaluate the difference between treatments, controlling for duration of disease category and baseline MGS score category.

Change from baseline in MGYLS at Day 14 and Month 1.5 will be analyzed as described for Month 3 in [Section 8.1.1](#).

Change from baseline in OSDI total score at Day 14 and Month 1.5 will be analyzed as described for Month 3 in [Section 8.1.1](#).

8.3. Exploratory Efficacy Analyses

The following endpoints will be presented using the ITT Set, unless otherwise specified. Where applicable, actual values and changes from baseline will be summarized descriptively for all time points at which the endpoint is collected.

8.3.1. Exploratory Efficacy Analyses Performed at Month 3

Proportion of MGYLS responders based on MGYLS > 2 will be analyzed through Month 3 as described for the proportion of MGYLS responders, using a CMH test (or chi-square/Fisher's Exact if CMH is not estimable) to evaluate the difference between treatments, controlling for duration of disease category and baseline MGS score category.

Change from baseline in MGYOLS at Day 14, Month 1.5 and Month 3 will be analyzed as described for MGYLS in [Section 8.1.1](#).

Proportion of MGYOLS responders based on MGYOLS >2 will be analyzed through Month 3 as described for the proportion of MGYLS responders, using a CMH test (or chi-square/Fisher's Exact if CMH is not estimable) to evaluate the difference between treatments, controlling for duration of disease category and baseline MGS score category.

Proportion of OSDI responders based on a reduction of >4.5 will be analyzed through Month 3 as described for the proportion of MGYLS responders, using a CMH test (or chi square/Fisher's Exact if CMH is not estimable) to evaluate the difference between treatments, controlling for duration of disease category and baseline MGS score category.

Change from baseline in OSDI subscales at Day 14, Month 1.5 and Month 3 will be analyzed as described for MGYLS in [Section 8.1.1](#).

Proportion of SPEED responders based on SPEED <6 will be analyzed through Month 3 as described for the proportion of MGYLS responders, using a CMH test (or chi-square/Fisher's Exact if CMH is not estimable) to evaluate the difference between treatments, controlling for duration of disease category and baseline MGS score category.

Change from baseline in TBUT at Day 14, Month 1.5 and Month 3 will be analyzed as described for MGYLS in [Section 8.1.1](#).

Proportions of TBUT >5 and >10 responders will be analyzed through Month 3 as described for the proportion of MGYLS responders, using a CMH test (or chi-square/Fisher's Exact if

CMH is not estimable) to evaluate the difference between treatments, controlling for duration of disease category and baseline MGS score category.

Change from baseline in Average VAS and Worst VAS at Day 14, Month 1.5 and Month 3 will be analyzed as described for MGYLS in [Section 8.1.1](#).

Proportion of Average VAS responders based on decrease ≥ 5 and proportion of Worst VAS responders based on decrease ≥ 5 will be analyzed through Month 3 as described for the proportion of MGYLS responders, using a CMH test (or chi-square/Fisher's Exact if CMH is not estimable) to evaluate the difference between treatments, controlling for duration of disease category and baseline MGS score category.

Change from Schirmer's assessment at Day 14, Month 1.5 and Month 3 will be analyzed as described for MGYLS in [Section 8.1.1](#).

Proportion of Schirmer's ≥ 10 mm responders will be analyzed through Month 3 as described for the proportion of MGYLS responders, using a CMH test (or chi-square/Fisher's Exact if CMH is not estimable) to evaluate the difference between treatments, controlling for duration of disease category and baseline MGS score category.

Change from baseline in Burning/Stinging VAS, Itching VAS, Foreign Body Sensation VAS, Eye Discomfort VAS, Photophobia VAS, and Pain VAS at Day 14, Month 1.5 and Month 3 will be analyzed as described for MGYLS in [Section 8.1.1](#).

Proportion of patients with clinical cure, defined as having MGYLS change from baseline ≥ 5 and OSDI total score < 13 , will be analyzed through Month 3 as described for the proportion of MGYLS responders, using a CMH test (or chi-square/Fisher's Exact if CMH is not estimable) to evaluate the difference between treatments, controlling for duration of disease category and baseline MGS score category.

Eyelid margin erythema and telangiectasias results will be summarized by time point, in conjunction with other findings from the slit lamp examination. Actual values and shifts from baseline through Month 3 will be summarized by parameter and time point. Changes from baseline will be analyzed at each time point using CMH statistics to evaluate the differences between each AZR-MD-001 treatment group and placebo, controlling for baseline value, using the following pseudocode:

```
PROC FREQ data=xxx;
  BY visit;
  TABLE treatment * base * result / CMH;
  ODS output CMH=outcmh (where=(ALTHYPOTHESIS='General Association'));
run;
```

Corneal and conjunctival staining (sodium fluorescein corneal staining and lissamine green conjunctival staining) are assessed on a 6-point scale using grades 0, I, II, III, IV, and V, and are summarized by grade and shift from baseline. Shift from baseline through Month 3 will be analyzed using CMH statistics as described for eyelid margin erythema and telangiectasias.

8.3.2. Exploratory Efficacy Analyses Performed at Month 6

These analyses will be performed using the ITT, mITT, and PP6 sets, as indicated. P-values will be provided for descriptive purposes only.

Change from baseline in MGYLS at Month 4.5 and Month 6 will be analyzed as described for MGYLS in [Section 8.1.1](#). This analysis will utilize multiple imputation based on data from the entire 6-month study duration, as described in [Section 5.3.1.2](#), on the ITT, mITT, and PP6 sets. It will be repeated using LOCF on the ITT Set, as described in [Section 8.1.2.1](#).

Change from baseline in OSDI total score at Month 4.5 and Month 6 will be analyzed as described for MGYLS in [Section 8.1.1](#). This analysis will utilize multiple imputation based on data from the entire 6-month study duration, as described in [Section 5.3.1.2](#), on the ITT, mITT, and PP6 sets. It will be repeated using LOCF on the ITT Set, as described in [Section 8.1.2.1](#). Additionally, an analysis of potentially confounding medication, as described in [Section 8.1.2.2](#), will be performed at Month 6, utilizing the ITT Set with multiple imputation.

Proportion of MGYLS responders based on change from baseline ≥ 5 at Month 4.5 and Month 6 will be analyzed as described in [Section 8.2.1](#), using a CMH test (or chi-square/Fisher's Exact if CMH is not estimable) to evaluate the difference between treatments, controlling for duration of disease category and baseline MGS score category.

Proportion of OSDI responders based on OSDI total score < 13 at Month 4.5 and Month 6 will be analyzed as described in [Section 8.2.1](#), using a CMH test (or chi-square/Fisher's Exact if CMH is not estimable) to evaluate the difference between treatments, controlling for duration of disease category and baseline MGS score category.

Change from baseline in SPEED score at Month 4.5 and Month 6 will be analyzed as described for MGYLS in [Section 8.1.1](#).

Change from baseline in individual VAS scores, Average VAS, and Worst VAS at Month 4.5 and Month 6 will be analyzed separately as described for MGYLS in [Section 8.1.1](#).

Change from baseline in MGS at Month 4.5 and Month 6 will be analyzed using an ANCOVA model with (continuous) baseline MGS score as a covariate, and treatment and duration of disease category as factors, as described in [Section 8.2.2](#).

Proportion of MGS responders based on MGS >12 at Month 4.5 and Month 6 will be analyzed as described for the proportion of MGYLS responders, using a CMH test (or chi-square/Fisher's Exact if CMH is not estimable) as described in [Section 8.2.2](#).

Proportion of MGYLS responders based on MGYLS > 2 at Month 4.5 and Month 6 will be analyzed as described for the proportion of MGYLS responders, using a CMH test (or chi-square/Fisher's Exact if CMH is not estimable), as described in [Section 8.2.2](#).

Change from baseline in MGYOLS at Month 4.5 and Month 6 will be analyzed as described for MGYLS in [Section 8.1.1](#).

Proportion of MGYOLS responders based on MGYOLS > 2 at Month 4.5 and Month 6 will be analyzed as described for the proportion of MGYLS responders, using a CMH test (or chi-square/Fisher's Exact if CMH is not estimable), as described in [Section 8.3.1](#).

Proportion of OSDI responders based on a reduction of >4.5 at Month 4.5 and Month 6 will be analyzed as described for the proportion of MGYLS responders, using a CMH test (or chi square/Fisher's Exact if CMH is not estimable), as described in [Section 8.3.1](#).

Change from baseline in OSDI subscales at Month 4.5 and Month 6 will be analyzed as described for MGYLS in [Section 8.1.1](#).

Proportion of SPEED responders based on SPEED <6 at Month 4.5 and Month 6 will be analyzed as described for the proportion of MGYLS responders, using a CMH test (or chi-square/Fisher's Exact if CMH is not estimable), as described in [Section 8.3.1](#).

Change from baseline in TBUT at Month 4.5 and Month 6 will be analyzed as described for MGYLS in [Section 8.1.1](#).

Proportions of TBUT >5 and >10 responders at Month 4.5 and Month 6 will be analyzed as described for the proportion of MGYLS responders, using a CMH test (or chi-square/Fisher's Exact if CMH is not estimable), as described in [Section 8.3.1](#).

Proportion of Average VAS responders based on decrease ≥ 5 and proportion of Worst VAS responders based on decrease ≥ 5 at Month 4.5 and Month 6 will be analyzed as described for the proportion of MGYLS responders, using a CMH test (or chi-square/Fisher's Exact if CMH is not estimable) to evaluate the difference between treatments, controlling for duration of disease category and baseline MGS score category.

Change from Schirmer's assessment at Month 4.5 and Month 6 will be analyzed as described for MGYLS in [Section 8.1.1](#).

Proportion of Schirmer's ≥ 10 mm responders at Month 4.5 and Month 6 will be analyzed as described for the proportion of MGYLS responders, using a CMH test (or chi-square/Fisher's Exact if CMH is not estimable), as described in [Section 8.3.1](#).

Proportion of patients with clinical cure, defined as having MGYLS change from baseline ≥ 5 and OSDI total score < 13 , will be analyzed at Month 4.5 and Month 6 as described for the proportion of MGYLS responders, using a CMH test (or chi-square/Fisher's Exact if CMH is not estimable), as described in [Section 8.3.1](#).

Eyelid margin erythema and telangiectasias changes from baseline will be analyzed at Month 4.5 and Month 6, using CMH statistics as described in [Section 8.3.1](#).

Corneal and conjunctival staining shifts from baseline will be analyzed using CMH statistics, as described in [Section 8.3.1](#).

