5.3. Missing Data

Missing efficacy data will be handled as follows:

- The primary efficacy analyses and most other efficacy analyses will utilize multiple imputation.
- Sensitivity analyses will be performed on the primary using the LOCF approach, where non-missing post-baseline values are carried forward to subsequent visits.

Prior to performing imputation or analyses, results from unscheduled visits and early termination (ET) visits (defined as per [Section 5.1](#)) will be mapped to the closest scheduled visit (Day 14, Month 1.5, Month 3, Month 4.5, or Month 6). In other words, a patient with an ET visit at Day 40 would have its those results mapped to the Month 1.5 visit.

Actual item results will be imputed, and any subscale scores, total scores, changes from baseline, responder status, etc. will be derived from the imputed values where necessary.

For safety analyses, where incomplete dates are present, medications will be categorized as concomitant, and adverse events as treatment-emergent, unless sufficient information is present to definitely determine that the medication usage completed, or event resolved, prior to the first dose of study medication.

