5.3.1.1. Multiple Imputation for Primary Analysis

Multiple imputation will be performed separately for each assessment; in other words, MGYLS values will not be used to impute OSDI values. The same seed number (utilized in SAS[®] PROC MI) of 135790 will be used throughout. For each MI, 20 imputations will be created, analyses performed on each imputed dataset separately, and results combined using PROC MIANALYZE. The appropriate minimum and maximum values will be used for each variable, and results rounded to the same precision as collected values. Multiple imputation will be limited to patients in the analysis population being used, and will include values that are eligible for use in summaries and analyses as described in [Section 5.1](#) (e.g., unscheduled and early termination visits will be mapped to scheduled visits, and visits with >1 non-missing values mapped to that visit will utilize the later result), through the Month 3 visit. Screening visit values will not be incorporated into the multiple imputation.

The following variables will be included in the multiple imputation model, as numeric variables:

- Treatment group (split into three dichotomous variables)
- Randomization criteria (disease duration category and baseline MGS score category)
- Age
- Sex
- Analysis value (MGYLS or OSDI total score) for each scheduled visit

The following pseudocode will be used:

```
proc mi data=xxx seed=135790 nimpute=20 out=yyy  
    minimum = 0 0 0 18 0 0 0 0 0 0 0
```

```

        maximum = 1 1 1 99 1 1 1  xx xx xx xx
        round =   1 1 1 1  1 1 1  1  1  1  1  ;
var Dur5yr MGSless6 male age trt0_5 trt1_0 trtpbo
    Day1 Day14 Day45 Day90;
mcmc chain=multiple displayinit;
run;

```

<proc genmod, etc.>

```

Proc mianalyze data=xxx (drop=effect);
  by trt01pn;
  modeleffects LSM;
  stderr;
run;

```

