5.3.1.2. Multiple Imputation for Exploratory Analyses

A second multiple imputation will be performed similarly for each assessment, utilizing the data through Month 6, for exploratory efficacy analyses performed after the completion of the safety follow-up period. For each of the initial 20 imputations created through Month 3, an additional 20 imputations will be created to impute Month 4.5 and Month 6. Subsequent analyses of the 20×20=400 imputations will be performed separately for each imputation, then results combined using PROC MIANALYZE.

The following pseudocode will be used, in addition to the prior pseudocode:

```

proc mi data=yyy (rename=( _imputation_ =Imp1)) seed=1357902 nimpute=20 out=zzz
  minimum = 0 0 0 18 0 0 0  0  0  0  0  0  0
  maximum = 1 1 1 99 1 1 1  xx xx xx xx xx xx
  round =   1 1 1 1  1 1 1  1  1  1  1  1  1 ;

  by Imp1;

var Dur5yr MGSless6 male age trt0_5 trt1_0 trtpbo
    Day1 Day14 Day45 Day90 Day135 Day180;

mcmc chain=multiple displayinit;
run;

```

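### Clinical cure needs MGYLS and OSDI response in the same patient, but the SAP imputes the two separately with no pairing rule, so the cure rate may be biased slightly in a direction the documents do not settle

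*SAP*

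**What the plan says.** SAP 8.3.1 defines the endpoint as the "Proportion of patients with clinical cure, defined as having MGYLS change from baseline" of at least 5 glands combined with an OSDI total score below 13. It sends the analysis to the method for MGYLS responders, a stratified CMH test. SAP 8.3.2 repeats this for Month 4.5 and Month 6.

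On missing data, SAP 5.3 states: "The primary efficacy analyses and most other efficacy analyses will utilize multiple imputation". It adds that "responder status, etc. will be derived from the imputed values where necessary".

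SAP 5.3.1.1 then sets the imputation rule: "Multiple imputation will be performed separately for each assessment; in other words, MGYLS values will not be used to impute OSDI values". The outcome term in each model is "Analysis value (MGYLS or OSDI total score) for each scheduled visit", next to treatment, the two stratification categories, age and sex. For the later visits, SAP 5.3.1.2 says: "A second multiple imputation will be performed similarly for each assessment".

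No section says how a patient's imputed MGYLS and imputed OSDI values are to be combined into a cure status.

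**The concern.** Separate imputation suits an analysis that uses one endpoint at a time. Clinical cure uses two at once. When one or both components are missing, whether a patient counts as cured depends on the joint distribution of the two outcomes, and separate runs estimate only the two marginal distributions given their covariates. Matching the runs by imputation number does not help, because the draws were made without reference to each other. The same applies to a patient whose Month 3 MGYLS is observed and whose OSDI is missing: the observed gland response does not inform the imputed symptom score.

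Clinical cure is the SAP endpoint that joins the two primary outcomes within a patient. A distortion of its rate, or of the difference between arms, would bear on any statement about how many patients improve on both.

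**Working it through.** **Does imputation apply to cure?** SAP 8.3 does not restate it. SAP 8.3.1 refers to the MGYLS responder analysis in 8.2.1, which falls under the multiple-imputation statement in 8.2, and SAP 5.3 applies imputation to most other efficacy analyses without exempting cure. Imputation is the likelier reading, but it is not explicit.

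**Input check.** The plan states no cure rate, so there is none to reproduce. The SAP 2.3.1 Table 1 inputs can be checked against the SAP 2.3.2 power: MGYLS difference 2.77 - 0.77 = 2.0, SD 3.63, 75 per arm, two-sided 0.05. The noncentral t gives 0.918, as stated.

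**Inputs from Table 1**, Month 3 change, mean (SD):
- MGYLS: 0.5% 2.77 (3.35); 1.0% 3.79 (4.11); placebo 0.77 (2.28)
- OSDI: 0.5% -8.36 (9.06); 1.0% -5.33 (8.39); placebo -0.81 (6.31)

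**Assumptions not in the documents:**
- Changes are normal, with MGYLS rounded to whole glands (so at least 5 means above 4.5).
- Baseline OSDI is uniform on 13 to 34.
- Values of one endpoint at different visits correlate 0.4 (0.6 as a variant).
- Patients missing Month 3 split equally between no post-baseline visit, Day 14 only, and Day 14 plus Month 1.5.
- r, the correlation of the two improvements within a patient, runs from -0.2 to +0.5.
- 10% are missing at Month 3.

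**Step 1: marginal rates.** In the 0.5% arm, P(MGYLS change at least 5) = 1 - Φ((4.5 - 2.77)/3.35) = 0.303. Averaging over baseline, P(OSDI below 13) = 0.424. The product is 0.128, which is the cure rate under independence. The 1.0% arm gives 0.431 × 0.313 = 0.135, and placebo 0.051 × 0.140 = 0.007.

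**Step 2: rate among patients missing Month 3.** Simulation with at least one million patients per setting, 0.5% arm. Each endpoint is drawn given its own earlier visits only (separate) and compared with the full data:

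| r | Full data | Separate imputation | Whole-arm shift at 10% missing |
|---|---|---|---|
| -0.2 | 10.6% | 12.5% | +0.2 points |
| 0 | 12.8% | 12.8% | 0 |
| +0.1 | 14.0% | 13.0% | -0.1 |
| +0.3 | 16.3% | 13.2% | -0.3 |
| +0.5 | 18.6% | 13.5% | -0.5 |

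Whole-arm shift = fraction missing × (separate - full). For example, 0.10 × (13.2 - 16.3) = -0.31 points.

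**Step 3: other arms and settings.** The 1.0% arm also shifts by +0.2 to -0.5 points. Placebo shifts by less than +0.1 to -0.1, so the active-minus-placebo difference moves by about +0.2 to -0.4. With a visit correlation of 0.6 the 0.5% range narrows to +0.16 to -0.42. At 20% missing and r = +0.5 the 0.5% arm shift is -1.03.

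**Step 4: joint imputation.** At r = +0.3 and visit correlation 0.5, the 0.5% arm rate among patients missing Month 3 is 16.2% in full data, 13.5% with separate runs and 16.2% with a joint model. In the 1.0% arm the figures are 16.9%, 14.1% and 16.9%.

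**The case against.** The case for leaving the plan alone is strong on size. One patient in 75 is 1.3 points, and the standard error of a 15% rate is √(0.15 × 0.85/75) = 4.1 points, so the shift at 10% missing is less than half a patient per arm. Cure is exploratory, lies outside the testing hierarchy in SAP 8.1.1, and is absent from the endpoint lists in SAP 3.1.3. Month 4.5 and Month 6 p-values are descriptive only. All of this stands and makes the point minor. It does not remove the mismatch between a two-outcome endpoint and one-outcome imputation models.

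A reader might infer that cure rates must come out too low. The documents do not support that. They give no within-patient correlation, and in Table 1 the doses rank in opposite order: 1.0% is better on MGYLS, 0.5% on OSDI. That between-arm pattern does not settle the within-patient sign, but nothing else in the documents does either.

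A reader might also infer that the link between the two outcomes is lost altogether. It is not. Arm, strata, age, sex and each endpoint's own earlier visits are in the models, and association running through them is kept. Only the residual part drops out.

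**Conclusion.** The mismatch is real and follows from the SAP's own text, on the likelier reading that cure is derived from imputed data. The resulting bias is conditional: downward if sign and symptom improve together, absent if they are uncorrelated, upward if they move in opposite directions. Under the assumed range (r from -0.2 to +0.5, 10% missing) it is about +0.2 to -0.5 points per active arm. Joint improvement is clinically plausible, but it is an assumption. The primary analyses and the single-endpoint responder analyses are unaffected.

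Two further inferences should not be drawn. The common Month 3 seed "of 135790 will be used throughout" might suggest that the MGYLS and OSDI draws line up. Whether they would depends on the software and the data layout, and the documents do not show it. Likewise, SAP 12 might be read as having loosened cure by removing an MGS requirement. Protocol 9.4.3 lists separate cure proportions rather than requiring MGS above 12, SAP 12 discloses the redefinition, and MGS above 12 remains a secondary endpoint.

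**What to change.** For clinical cure only, derive the composite from a joint imputation that puts the MGYLS and OSDI columns in the same PROC MI VAR list. Do this once through Month 3 (for 8.3.1) and once in the nested Month 4.5/6 step (for 8.3.2). Add a sentence to SAP 8.3 confirming that cure uses imputed data and that both components come from the same imputed data set. Leave the single-endpoint imputations as they are.

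The cost is SAP wording and two further PROC MI calls, specified before unmasking. The Month 3 model grows from 11 variables (7 covariates and 4 visit columns) to 15 (7 + 8), and the Month 6 model from 13 to 19 (7 + 12). The downside to accept is that cure would rest on different imputed values from the MGYLS and OSDI responder tables, so the cure rate may not reconcile exactly with its components. A table footnote should say so.

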8. EFFICACY

Efficacy analyses will be performed on the ITT Set. The primary analyses will be repeated on the mITT Set (if different from the ITT Set) and PP Set. If the primary analyses are notably different between the ITT and mITT sets, additional analyses of the other efficacy endpoints may be performed on the mITT Set.

In addition to those analyses, which are performed at the 3-month time point, additional exploratory analyses will be performed at the 6 month time point, using data collected during the 3 month safety follow-up period. These analyses will also be performed on the ITT Set, with MGYLS and OSDI total score analyses repeated on the mITT and PP6 sets. P-values for analyses of data collected during the 3-month safety follow-up period (e.g., Month 4.5 and Month 6) are provided for descriptive purposes only.

Endpoints will be summarized descriptively, for all scheduled assessment time points. Actual values and changes from baseline will be summarized descriptively for all time points at which the endpoint is collected.

Dichotomous endpoints will be analyzed using a CMH test to compare each AZR-MD-001 treatment arm to placebo, controlling for disease duration category and baseline MGS score category. If CMH comparisons are not estimable, Pearson's chi-square or Fisher's Exact will be used, as described in [Section 8.2](#) and [Section 8.3](#).

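### The CMH code for lid-margin signs and staining stratifies by treatment and tests baseline grade against later grade, so it does not compare either dose with placebo

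*SAP*

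**What the plan says.** SAP 8.3.1 states that CMH statistics will be used "to evaluate the differences between each AZR-MD-001 treatment group and placebo, controlling for baseline value". The code given to carry this out is "TABLE treatment * base * result / CMH", and the General Association row is kept from the output.

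Other analyses point back to this method:

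- Corneal and conjunctival staining through Month 3 "will be analyzed using CMH statistics as described for eyelid margin erythema and telangiectasias" (SAP 8.3.1).
- In SAP 8.3.2, "Eyelid margin erythema and telangiectasias changes from baseline will be analyzed at Month 4.5 and Month 6, using CMH statistics", with a reference to 8.3.1.
- Also in SAP 8.3.2, "Corneal and conjunctival staining shifts from baseline will be analyzed using CMH statistics", again with a reference to 8.3.1.

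Elsewhere the SAP orders its CMH variables differently. The responder code in 8.2.1 is "TABLE baseMGS * duration * treatment * response/CMH", and the introduction to Section 8 says the CMH test for dichotomous endpoints is there "to compare each AZR-MD-001 treatment arm to placebo".

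**The concern.** The sentence and the code in 8.3.1 describe different tests, and the sentence hands its execution to the code. A programmer who follows the code gets a plausible p-value with no error message, and a reader of the table would take it as a dose-versus-placebo result.

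Lid-margin signs and staining grades can be expected to correlate with their own baseline. The coded test would then often be significant with an inert drug, and it would hardly respond to an active one.

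Two smaller wording points lie nearby.

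- **(a)** The responder code in 8.2.1 has the right order but shows no restriction to one dose plus placebo.
- **(b)** The conditional OSDI model for confounding medications in 8.1.2.2 is specified "with baseline MGYLS score as a covariate and treatment, duration of disease category, and baseline MGS score category as factors", whereas the primary OSDI model in 8.1.1 adjusts for the baseline OSDI total score.

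**Working it through.** The plan gives no figure for this analysis, so there is nothing to reproduce. The check has two parts.

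**1. What the code tests.** In a multiway PROC FREQ request the last two variables are crossed and all earlier ones are strata.

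| | Strata | Rows | Columns | Question answered |
|---|---|---|---|---|
| 8.2.1 responder code | baseline MGS category, duration | treatment | response | does response differ by treatment? |
| 8.3.1 code | treatment | baseline grade | later grade | does baseline grade predict later grade? |
| 8.3.1 text | baseline grade | treatment | later grade | does later grade differ by treatment? |

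The degrees of freedom of the general association statistic are (R−1)(C−1). With four grades the coded order has (4−1)(4−1) = 9, whether two or three arms are in the data, because treatment is neither row nor column. The order that the text requires has (2−1)(4−1) = 3 for one dose against placebo. Subsetting the data changes the number of strata in the coded order but not what is tested.

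**2. Size of the effect.** The statistic is Q = G′V⁻¹G. Here G sums observed minus expected counts over strata (last row and column dropped). V sums n²/(n−1) · [diag(p_r) − p_r p_r′] ⊗ [diag(p_c) − p_c p_c′], with p_r and p_c the row and column proportions in a stratum of n patients. Q is referred to chi-square.

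Inputs:

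- 75 per arm, from SAP 2.3.1.
- Six staining grades, from SAP 8.3.1.
- Exclusion of corneal staining of grade 3 or more, from Protocol 5.2.
- Assumed, because the documents do not give them: the correlations, the grade frequencies, a four-grade lid-margin scale and the effect size.

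Baseline and visit values were drawn from a bivariate normal distribution and cut into grades, with 2,000 trials per setting. At a true 5% rate the Monte Carlo standard error is √(0.05 × 0.95 / 2000) ≈ 0.5 percentage points.

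Percentage of trials with p<0.05:

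| Setting | Correlation | Coded, 3 arms | Coded, dose + placebo | Corrected, dose + placebo |
|---|---|---|---|---|
| No effect, 4 equal grades | 0 | 4.6 | 5.0 | 3.8 |
| | 0.3 | 79.2 | 56.6 | 4.4 |
| | 0.5 | 100 | 98.9 | 4.8 |
| 0.5 SD benefit in both doses, 4 grades | 0 | 4.6 | 4.4 | 64.3 |
| | 0.3 | 77.2 | 54.8 | 67.0 |
| | 0.5 | 100 | 98.7 | 73.6 |
| No effect, 6 grades (30/35/20/9/4/2%), baseline 0–II | 0 | 4.8 | 4.4 | 4.0 |
| | 0.3 | 51.8 | 33.2 | 3.4 |
| | 0.5 | 98.8 | 88.6 | 3.2 |

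The coded columns follow the correlation and ignore the drug. The corrected column holds its level with no effect and has power when there is one.

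A separate run used unequal four-grade cut-points, one dose plus placebo, 1,000 trials and correlations of 0, 0.3 and 0.6.

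- Coded order: 4.6%, 57.7% and 100% with no effect; 5.4%, 55.4% and 100% with a 0.6 SD effect.
- Corrected order: 4.4%, 4.5% and 4.4% with no effect; 79.8%, 83.4% and 92.4% with the 0.6 SD effect.
- A 1.0 SD effect at correlation 0: 4.1% coded, 99.9% corrected.

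**Points (a) and (b).** If the dataset in 8.2.1 held all three arms, the responder test would have (3−1)(2−1) = 2 degrees of freedom, an omnibus test and not the pairwise one described. For (b), adjusting OSDI change for baseline MGYLS leaves out the covariate expected to explain most of its variation. In a randomized comparison that mainly costs precision, and it was not quantified here.

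**The case against.** The strongest reply is about weight. The block is pseudocode, the sentence above it states the intended comparison clearly, and 8.2.1 shows that the authors know the right order. On a three-arm dataset the code returns one p-value per visit where the text needs two, so the slip might surface in programming. The endpoints are exploratory, and SAP 8 and 8.3.2 label the Month 4.5 and Month 6 p-values as descriptive. All of this stands and limits the severity. It does not make the code right: on dose-plus-placebo subsets the output looks normal, and the descriptive label does not cover Month 3.

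The reach to staining is less certain in the output list. Appendices 4 and 5 title the staining outputs (Tables 16 and 16.1) as shift tables only, while the lid-margin outputs (Tables 15A and 15A.1) are titled as shift table and analysis. Even so, the text of 8.3.1 and 8.3.2 sends staining to the same CMH test.

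The percentages rest on assumed inputs, and the six-grade scenario fits corneal staining only, because no matching exclusion is stated for conjunctival staining. This is fair: the figures illustrate the consequence and are not forecasts for this trial.

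Point (a) contradicts nothing, since the SAP usually states the pairwise restriction in text and its dataset name is a placeholder. Point (b) looks like carried-over wording: the code there uses the same generic baseline term as the primary model, and the analysis runs only if more than 10% of patients have confounding treatments. Both are clarifications.

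**Conclusion.** The concern holds. As coded, the analysis of lid-margin erythema and telangiectasia, and of the staining and later-visit endpoints that refer to it, does not test either dose against placebo. This follows from the variable order alone and needs no assumption.

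How often it would mislead depends on the unknown correlation of each grade with its own baseline. With no drug effect, at an assumed correlation of 0.3, false significance occurs in roughly one third to four fifths of trials across the table's scenarios. At 0.5 it occurs in nearly nine tenths or more. At zero correlation the test stays near 5% but has no power for the drug.

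No primary or key secondary analysis uses this code, and no alpha-controlled claim is affected. It should be corrected before the Month 3 outputs are produced.

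**What to change.** In SAP 8.3.1, replace the line with `TABLE base * treatment * result / CMH`, run separately on 0.5% plus placebo and on 1.0% plus placebo. The General Association statistic can stay. State that the same code applies to corneal and conjunctival staining and to Months 4.5 and 6, and align the titles of Tables 16 and 16.1 if staining p-values are to be shown.

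In the same edit:

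- **(a)** In 8.2.1, add a WHERE statement limiting each CMH and chi-square/Fisher run to one dose and placebo.
- **(b)** In 8.1.2.2, name the baseline OSDI total score as the covariate. Note also that the confounding-therapy indicator is measured after randomization and may itself be affected by treatment, so that sensitivity result needs cautious interpretation.

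The cost is SAP text and code edits only, with no new data and no additional analyses.
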